8. POTENTIAL BENEFITS TO SUBJECTS

There will be no direct benefit to the subjects. The therapy for NSCLC Subjects will not be changed based on the [¹⁸F]F-ArAG PET findings.

9. CONCOMITANT MEDICATIONS

Subjects must be questioned at each study visit concerning any new medications or changes in current medications including over-the-counter and topical medications. All medications and therapies administered or taken by the subject beginning 30 days prior to signing the ICF and throughout the study will be recorded in the source documents and on the appropriate page of the CRF. Intravenous fluid documentation will NOT include IV fluids used to administer medications, only the medications administered through the IV fluid will be documented. Intravenous fluids used to keep the vein open or used for flushing will also not be documented in the concomitant medication CRF.

For each medication and non-study treatment, the following will be documented:

- Medication/treatment name (generic name may be used if trade name is unknown)
- Dose, unit, and frequency of dosing (individual dosages, not total daily dose). Note: Each new dose of medication should be recorded as a separate entry, with the exception of medications that are given on a sliding scale. For these, it is acceptable to enter the range of the dosage, including the start and stop dates for which the specified dosage range was used.
- Route of dosing
- Indication for use (Indication should include exact medical terminology)
- The start date
- The stop date (if medication/therapy is not ongoing)

10. OUTCOME MEASURES AND ANALYSIS

10.1 Physiological Time-Activity Curves of [¹⁸F]F-ArAG Uptake within Healthy Tissues

One of the primary objectives of the study is to obtain baseline pharmacokinetic information in the form of [¹⁸F]F-ArAG uptake in healthy tissues as a function of time. To achieve this outcome, data on [¹⁸F]F-ArAG uptake in several tissue types will be collected from healthy subjects. This data will be presented in the form of time-activity curves (TAC) generated for each tissue type.

10.2 Time-Activity Curves of [¹⁸F]F-ArAG Uptake within Tumors and Background Tissues

Another objective of the study is to obtain pharmacokinetic information in cancer subjects in the form of relative [¹⁸F]F-ArAG uptake in tumor lesions and background tissues as a function of time. To achieve this outcome, data on [¹⁸F]F-ArAG uptake in tumor lesions and background activity in

the same tissues as in Section 10.1 will be collected. This data will be similarly presented in the form of time-activity curves (TAC) generated for each tissue type as in Section 10.1, as well as for tumor lesions against their background tissues.

10.3 Recommended time post [¹⁸F]F-AraG infusion to acquire a single static PET/CT scan

The TAC analysis of [¹⁸F]F-AraG uptake will provide insight into the earliest time to achieve adequate tumor versus non-malignant background tissue activity, as well as time to reach and remain in steady state up to 90 minutes. Such information can guide a recommendation for the ideal time window for a static [¹⁸F]F-AraG PET scan for future trials and potential clinical use.

10.4 Change in PET signal pre- and post- first dose of PD-1/PD-L1 immunotherapy

For NSCLC subjects who undergo two [¹⁸F]F-AraG PET/CT scans, the signal at a static time point post [¹⁸F]F-AraG infusion (obtained from the result of one of the outcome measures; Section 10.3) from both scans will be observed for trends.

10.5 Safety Outcome Measures

- Incidence of Treatment-Emergent Adverse Events (AEs).
- Incidence of withdrawals due to AEs.
- Serious Adverse Events (SAEs)

Analyses of safety outcomes will be conducted using the safety population. Adverse events will be coded using MedDRA. Treatment Emergent AE's (TEAE) are defined as events with an onset on or after the first treatment. TEAEs will be summarized by treatment group and by stage of the study, System Organ Class, and preferred term. The following TEAE summaries will be provided:

- TEAEs by severity grade
- TEAEs by relationship to study treatment.

In addition, separate summaries of serious adverse events, and adverse events resulting in discontinuation of study treatment will be presented.

10.6 Efficacy Outcome Analysis

Descriptive statistics will be used to summarize the characteristics of study participants, including their age, gender, primary tumor sites and clinical stages, concomitant medications, etc. Frequency tables will be used to summarize categorical variables. Median and inter-quartile ranges will be used to describe no-normally distributed continuous variables. Mean and standard deviation will be used to summarize normally distributed continuous variables.

Feasibility will be assessed per patient basis. The percentage of patients who can be successfully evaluated by [¹⁸F]F-AraG PET imaging will be computed and summarized.

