5. STUDY DESIGN

Protocol CST-FARAG-203 is a pilot study using the uEXPLORER total-body PET/CT system to acquire dynamic [¹⁸F]F-AraG scan data in healthy individuals and patients with NSCLC.

Screening will consist of eligibility confirmation, the patient signing the consent form, and any assessments outlined in the study calendars below. This will also include a query about status and date of COVID-19 vaccination.

Eligible healthy subjects will undergo a single dynamic [¹⁸F]F-AraG PET/CT scan (of duration up to 90-minutes) on the uEXPLORER PET/CT scanner within 28 days of screening or on the day of screening if possible and convenient to the subject. There will be a follow-up visit or call 7 days after the scan to assess any AEs that could be attributed to either the scan or the administration of [¹⁸F]F-AraG.

Eligible subjects with NSCLC who are planned to receive PD-1/PD-L1 immunotherapy will undergo a pre-therapy dynamic [¹⁸F]F-AraG PET/CT scan, and an optional post-therapy (first dose only) dynamic [¹⁸F]F-AraG PET/CT scan on the uEXPLORER total-body scanner.

For each enrolled patient, [¹⁸F]F-AraG will be administered by a licensed Nuclear Medicine technologist under the supervision of a board-certified Nuclear Medicine physician (ABNM or ABR certified) on an outpatient basis. It will be administered as a single bolus injection of 5 mCi +/-20% IV into a vein. Vital signs will be assessed just prior to and after completion of dynamic [¹⁸F]F-AraG PET scan.

For each scan, the subject will be prepared according to the site's standard procedures and asked to void the bladder immediately prior to imaging. For the scan, an intravenous (IV) line will be placed in a vein and the subject will be positioned supine on the scanner table. The PET/CT imaging will begin with a low-dose CT scan on the uEXPLORER PET/CT scanner. This CT scan will provide information for anatomic localization and attenuation correction purposes.

[¹⁸F]F-AraG will then be infused as above and a 90-minute dynamic PET scan will be performed on the uEXPLORER. The IV line will be removed after dynamic acquisition. For subjects who may not be able to undergo a 90-minute dynamic scan, a 60-minute dynamic PET scan will be performed, followed by a 10-minute static scan starting at 80 minutes post [¹⁸F]F-AraG infusion. The separate static scan at 80 minutes will be obtained along with an ultra-low-dose CT which is needed for attenuation correction of this separate scan.

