7. RISKS TO SUBJECTS

7.1.1 Risks from [¹⁸F]F-ArA/G PET/CT scan

In this study, 2-4 healthy subjects and 2-4 NSCLC patients will undergo research PET/CT imaging with [¹⁸F]F-ArA/G as specified in the experimental imaging section. [¹⁸F]F-ArA/G PET imaging has been performed on 6 healthy volunteers in a separate study with no drug-related side effects. In addition, [¹⁸F]F-ArA/G has been administered to 13 cancer patients with 7 of those patients getting two doses for pre and post immunotherapy scans, also without any drug-related side effects.

Given the prior clinical safety experience thus far, we expect few, if any, adverse effects from [¹⁸F]F-ArA/G administration in this study. Presently there are no standard surrogate biomarkers or imaging modalities that can substitute for these procedures. The alternative will be for the patient to withdraw from the imaging study.

The safety monitoring practices employed by this protocol are adequate to protect the subjects' safety and should detect all Treatment Emergent Adverse Events (TEAEs). An indirect health benefit to the subjects enrolled in this trial is the free medical tests received at screening and during the study.

Due to the (up to) 90-minute long scan time through which the participants are expected to remain still, the patients may feel discomfort and/or fatigue from laying on the scanner table. In addition, they may experience claustrophobia from being inside the scanner bore, which is a partially enclosed space.

Another risk is possible bruising and/or infection at the IV site.

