11.4.1 Efficacy population

The efficacy population is defined as all subjects who have received at least one (up to) 90-minute dynamic [¹⁸F]F-AraG PET scan.

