Appendix 2: Study Registration and Participant visits

- A. The subject will sign and date the Informed Consent Form (ICF), and Health Insurance Portability and Accountability Act (HIPAA) authorization (according to site's practices) prior to any study-related procedures with the exception of the standard-of-care (SOC) diagnostic/tumor staging CT or MRI that would be accepted for imaging review to assess eligibility of NSCLC subjects, if done within 45 days prior to Visit 2.
- B. Once signed, informed consent has been obtained; patients will be entered on study. To register a patient, the study coordinator must complete the Eligibility Checklist. The study coordinator will register the patient onto the study and assign a unique an Enrollment ID before initiation of the study drug administration.
- C. Pre-study laboratory tests must be completed prior to registration within the time frame specified in the protocol.
- D. A subject failing to meet all protocol requirements may not be registered. If you have any questions regarding eligibility, please contact the coordinating site PI or Study Coordinator
- E. Unscheduled visits may be required in addition to the scheduled visits per the Investigator's discretion. The details of these unscheduled visits with subjects will be recorded in the medical records and on the Case Report Form (CRF).
- F. If a subject misses a visit, the site is to make every effort to have the subject return as soon as possible to make up the visit. Once the subject is seen, he/she is to return to his/her original visit schedule.
- G. A subject who has signed the consent form but does not receive any [¹⁸F]F-AraG infusion is classified as a screen failure. Subject number, demographic information, and reason for screen failure will be collected.
- H. A subject who is classified as a screen failure will be replaced. A subject who does not receive at least one infusion of [¹⁸F]F-AraG and the associated PET/CT scans will also be replaced.

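### Does the feasibility percentage in section 10.6 hide subjects who could not be scanned, given that its denominator and its success criterion are not stated?

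*Combined protocol and SAP*

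**What the plan says.** Section 10.6, Efficacy Outcome Analysis, has two parts. The first describes participants (age, sex, tumor site, stage, concomitant medications) with descriptive statistics. The second assesses feasibility patient by patient: "The percentage of patients who can be successfully evaluated by [¹⁸F]F-AraG PET imaging will be computed and summarized". Neither part names an analysis population, and the documents nowhere define a successful evaluation.

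The provisions that bear on the figure are these:

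- Section 11.4.1 defines the efficacy population as "all subjects who have received at least one (up to) 90-minute dynamic [¹⁸F]F-AraG PET scan". The per-protocol set (11.4.2) is a subset of it. The safety population (11.4.3) requires at least one dose.
- Section 5 gives the order of events: "The PET/CT imaging will begin with a low-dose CT scan on the uEXPLORER PET/CT scanner", with the tracer given afterwards. For subjects who cannot manage 90 minutes, "a 60-minute dynamic PET scan will be performed, followed by a 10-minute static scan starting at 80 minutes post [¹⁸F]F-AraG infusion".
- Section 7.1.1 warns of participants that "they may experience claustrophobia from being inside the scanner bore, which is a partially enclosed space".
- Appendix 2, item G: "A subject who has signed the consent form but does not receive any [¹⁸F]F-AraG infusion is classified as a screen failure". Item H: "A subject who is classified as a screen failure will be replaced". Item H also replaces subjects who lack the infusion and its associated scans.
- Section 11.5.1 provides the disposition of everyone who signs consent, with a by-subject listing. Section 11.3 puts all collected data in listings.

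**The concern.** A feasibility rate should show how often the procedure fails. Read under its heading, 10.6 seems to take its percentage over the efficacy population, and a subject enters that population only by being scanned. Someone who cannot bear the bore at the CT step is never infused, becomes a screen failure, is replaced, and falls outside all three analysis populations. The percentage could then read 100% whatever the number of such failures.

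The numerator is open as well. The efficacy definition sets no explicit minimum scan length. A subject who completes the 60-minute dynamic scan but misses the later static scan could be counted either way. The choice has some substance, because section 10.3 looks for the "time to reach and remain in steady state up to 90 minutes" and that subject has no data after 60 minutes.

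At stake is whether a reader could take 100% as evidence that the long scan is tolerated, when section 2 itself supposes that cancer subjects will tolerate it less well than healthy volunteers.

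**Working it through.** The plan gives no expected feasibility rate, target or power calculation, so there is no stated figure to reproduce. The inputs are the planned group sizes (2 to 4 healthy, 2 to 4 NSCLC; section 11.1) and assumed failure counts of 0, 1 or 2, since the documents give no failure rates.

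**Step 1: is the efficacy denominator written?** It is not. Section 10.5 names the safety population for safety outcomes; 10.6 names none. The heading is weak evidence. The first paragraph under it includes concomitant medications, which section 11.5.3 assigns to the safety population, so the content of 10.6 is not tied to 11.4.1. A percentage over enrolled patients is an equally natural reading. What the text supports is that the denominator is unstated.

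**Step 2: how far do the readings differ?** Let n subjects be fully scanned and j fail before infusion and be replaced. Over the efficacy population the figure is n/n. Over all subjects brought to the scanner it is n/(n + j). Intervals are exact (Clopper-Pearson) 95%; when x = n the lower limit is 0.025^(1/n), for example 0.025^(1/4) = 39.8%.

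| n | j | efficacy population | brought to the scanner |
|---|---|---|---|
| 4 | 0 | 4/4 = 100% (39.8 to 100) | 4/4 = 100% (39.8 to 100) |
| 4 | 1 | 4/4 = 100% (39.8 to 100) | 4/5 = 80.0% (28.4 to 99.5) |
| 4 | 2 | 4/4 = 100% (39.8 to 100) | 4/6 = 66.7% (22.3 to 95.7) |
| 2 | 1 | 2/2 = 100% (15.8 to 100) | 2/3 = 66.7% (9.4 to 99.2) |
| 2 | 2 | 2/2 = 100% (15.8 to 100) | 2/4 = 50.0% (6.8 to 93.2) |

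Every figure in the last column lies inside the interval around the 100% beside it.

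**Step 3: partial scans.** If one of four scanned subjects misses the 80-minute static scan, the result is 4/4 = 100% or 3/4 = 75.0% (19.4 to 99.4). With one of two it is 2/2 = 100% or 1/2 = 50.0% (1.3 to 98.7). If everyone completes a planned acquisition, completion-based readings agree at 100%.

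**Step 4: would the obvious repair help?** Taking all infused subjects as the denominator does not recover the lost cases. The j subjects in Step 2 were not infused, so the figure stays at 4/4 = 100% for any j. That repair adds only subjects infused but not scanned, who should be rare because infusion takes place on the scanner.

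**Step 5: are the losses visible elsewhere?** Appendix 2, item G, collects the reason for each screen failure. Section 11.5.1 counts subjects screened, enrolled, completed and discontinued and lists them individually. Section 11.3 lists all collected data. Item B of Appendix 2 has subjects registered before the tracer is given, so a failure at the CT step may also appear as an enrolled subject who discontinued, with the reason recorded (13.5). For a partial scan, the time-activity curve itself stops early.

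**The case for a change.** The best case for a change is that the plan promises this number and readers will take it as a feasibility rate. A subject who fails before infusion is outside all three defined populations, so the main example does not depend wholly on inferring the efficacy set. The partial-scan question needs no inference at all, and leaving it open until the data are seen allows a choice between 100% and 75%. Section 11.5.1 summarizes reasons for discontinuation after enrollment, whereas an uninfused subject is labelled a screen failure, so the link to feasibility is not explicit. Healthy and NSCLC subjects might also be pooled. A few sentences would settle all of this at almost no cost.

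Most of that is accurate as description: neither the denominator nor the criterion is stated. It does not show that a conclusion would be wrong. Reasons for screen failure are collected and therefore listed. Sections 11.5.1 and 11.5.2 already separate the two groups, and an analyst would do the same here. Assessment per patient in 10.6, with at least one scan in 11.4.1, leaves little reason to count the optional second scan as a separate unit.

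Nor is completed acquisition clearly the right criterion. Section 4.1, item 8, and section 11.1 point instead to whether a lesion can be quantified, and under that reading a completed scan with no quantifiable lesion would not be a success. Choosing between these readings is for the sponsor.

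**Conclusion.** The gap is one of detail in a descriptive percentage, and it calls for no change. Feasibility does not appear among the objectives (3.1, 3.2) or in the outcome measures listed in the synopsis, and no threshold or decision rests on it. The primary results are time-activity curves and a recommended imaging window, and neither uses this figure.

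The possible discrepancy looks large in percentage points: 100% against 80% or 67% with four scanned, 100% against 67% or 50% with two, and 100% against 75% for one partial scan among four. Each represents only one or two people, under assumed failure counts, and those people are individually visible in the disposition summary and listings. An analyst would reasonably report x out of n by group, say what n is, and mention any failed attempts alongside.

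This conclusion rests on two assumptions: that the by-subject listings are produced as planned, with reasons for screen failure included, and that the percentage is not later used as a standalone claim about how well the scan is tolerated.

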11. STATISTICAL METHODS AND DATA ANALYSIS

11.1 Number of Subjects

The primary goal of this pilot study is to acquire preliminary dynamic [¹⁸F]F-AraG scan data in healthy individuals and patients with NSCLC. Given the preliminary nature of this study, a power calculation was not performed. 2-4 subjects are likely sufficient for a general understanding of healthy tissue uptake as a function of time. Similarly, 2-4 NSCLC subjects are considered adequate to provide at least one lesion with positive and sufficient tumor uptake of [¹⁸F]F-AraG to provide a general understanding of tumor tracer kinetics.

11.2 Scan Data

Data from uEXPLORER scanner will be acquired in listmode. Data will be reconstructed using manufacturer's recommendations. Image quality, quantitative comparisons and preliminary biodistribution data collection will be performed by means of volumes of interest (VOIs) drawn in different organs, tissue types and tumor lesions (in NSCLC subjects). These will be used to generate standard uptake values, normalized to body weight (SUV-bw) for the purpose of quantitative analysis of spatial as well as temporal tracer distribution.

11.3 General Statistical Considerations

All collected study data will be presented in subject data listings. Descriptive statistics (n, mean, standard deviation, median, minimum and maximum) will be presented for continuous variables. Frequencies and percentages will be presented for categorical variables.

11.4 Analysis populations

The details of the analysis population to be used for the study are described below:

11.4.1 Efficacy population

The efficacy population is defined as all subjects who have received at least one (up to) 90-minute dynamic [¹⁸F]F-AraG PET scan.

11.4.2 Per-protocol (PP) Population

The Per Protocol (PP) population is defined as the set of subjects who meet the efficacy population requirements and were not associated with a major protocol violation.

11.4.3 Safety Population

The Safety population is defined as all subjects receiving at least one dose of [¹⁸F]F-AraG.

11.5 Statistical Methods

11.5.1 Subject Disposition

The disposition of all subjects who sign an ICF will be provided. The numbers of subjects screened, enrolled, completed, and discontinued during the study, as well as the reasons for all post-

enrollment discontinuations will be summarized for healthy and NSCLC subjects respectively. Disposition and reason for study discontinuation will also be provided as a by-subject listing.

11.5.2 Demographics and baseline characteristics analysis

Demographics and baseline characteristics will be summarized for healthy and NSCLC subjects respectively using appropriate descriptive statistics.

11.5.3 Concomitant Medications/Therapies

Concomitant medications/therapies will be summarized separately for the Safety population. All prior and concomitant medications recorded in the case report form will be coded to all matching Anatomic Therapeutic Classification codes using the most recent version of WHO Drug. Descriptive summaries, by study group and stage of the study, will be prepared using the coded term. All concomitant medications/therapies recorded in the case report form will be listed.

11.5.4 Medical history

The medical history will be summarized and/or listed descriptively.

11.5.5 Study Treatment Compliance

The study treatment compliance data will be summarized and/or listed descriptively.

12. SAFETY REPORTING OF ADVERSE EVENTS

12.1 Assessment of Safety

The Investigator is responsible for the detection and documentation of events meeting the criteria and definition of an AE or SAE, as provided in this protocol. During the study when there is a safety evaluation, the Investigator or site staff will be responsible for detecting, documenting and reporting AEs and SAEs as detailed in this Section of the protocol.

12.2 Adverse Events

An adverse event (AE) is defined as any unfavorable or unintended sign, symptom, or disease that occurs or is reported by the patient to have occurred, or a worsening of a pre-existing condition. An adverse event may or may not be related to the study treatment.

AEs will be elicited through direct questioning and subject reports. Any abnormality in physical examination findings or laboratory results that the investigator believes is clinically significant to the research subject and that occurred after initiation of the first study treatment will be reported as AEs. Abnormal findings that are NOT clinically significant should not be recorded as an AE.

